3.4. Outcome analysis

3.4.1. Primary Analysis

All analyses will be run as both intent-to-treat (ITT, i.e., group that the participant was randomized to) and per protocol (i.e., group participant actually participated in*). SAS Version 9.4³⁵ or later will be used for all analyses. For non-inferiority analyses, a successful result will be based on the upper bound of the 95% confidence interval being less than or equal to the non-inferiority margin. Based on recent guidelines^{28, 29}, we will not adjust our two primary hypotheses for multiplicity as they do not involve different endpoints (i.e. both hypotheses test EPDS scores). For secondary superiority hypotheses, a two-sided significance level of $p<0.05$ will be used to denote statistical significance. Descriptive statistics will be calculated for all variables of interest. Continuous measures such as age and depressive symptoms will be summarized using means and standard deviations, whereas categorical measures will be summarized using counts and percentages.

*Note: The trial has n=21 protocol deviations. This number has been consistent since the last major COVID wave (March 2022).

Demographic (e.g., ethnicity, age, marital status) and other baseline variables (e.g., severity and chronicity) will be compared for potential differences between study groups (TM vs IP, and SP vs NSP) using two sample two sided t-tests for continuous variables (or Wilcoxon rank sum test in the case of non-normal data), and chi-square analyses for categorical variables (Fisher's exact tests in the case of low expected cell sizes). Those who withdrew from the trial will be compared to those who continued on baseline indices including maternal education and occupation.

The primary outcome of non-inferiority in EPDS scores will be compared between NSP vs. SP and TM vs. IP groups at 3-months using a t-test with a 10% and 13% margins of non-inferiority, respectively.

Primary Aim 1: Examine if a brief, BA psychological treatment delivered by non-specialist providers (NSP) is as effective in treating perinatal depressive symptoms as specialist-delivered treatment.

Aim 1 is to show that NSP is non-inferior to SP (N=479 per group, SPs vs NSPs, [Table 3](#)).

Primary Aim 2: Examine if a brief BA psychological treatment delivered through telemedicine (TM) is as effective in treating perinatal depressive symptoms as in-person treatment (IP).

Aim 2 is to show that TM is non-inferior to in-person (N=268 per group, IP vs TM, [Table 4](#)).

Aim 1 and Aim 2 will initially be analyzed using a non-inferiority t-test (under the assumption that randomization will serve to balance out potential confounders). Each t-test will look at the confidence interval around the difference in EPDS scores (say between TM and IP) and see if the upper bound contains the non-inferiority margin (upper bound for the case in which we take the difference to be TM minus IP). In addition, we will run a linear regression model with mode, agent, and a mode by agent interaction term to assess whether an interaction between mode and agent exists. In the unlikely event that randomization was not able to reduce bias by balancing out confounders, we will adjust for variables found to be imbalanced at baseline.

Rules on the number of variables allowed in a multivariable model will be followed. The rule on number of variables in a **linear** regression is to take the total number of observations divided by 10. Given our trial sample size, we do not have any concerns with overfitting our linear model for our **covariates of interest** (education level, marital status, ethnicity, baseline severity and chronicity, timing of treatment, compliance, perceived support, and medication). For the **logistic** regression analyses, the number of predictors will be based on the smaller of the two outcome categories divided by 10^{36} .

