#### 2.2. Treatment and Intervention Arms

- **2.2.1. Treatment.** The intervention will consist of six to eight weekly sessions of BA delivered to each participant individually. The current manual (*Appendices B1 and B2 Treatment Manual and The PREMIUM Counselling for Relationships Manual, respectively*)) have been adapted from two well-established and tested manuals— the Alma Program for perinatal populations in Colorado and the Healthy Activity Program (HAP) from Goa, India, respectively. BA posits that the key to feeling less depressed is to increase enjoyable or fulfilling activities that align with one's values and targeting the mechanisms of patient activation. Unlike other cognitive behavioral interventions for depression, BA explicitly targets avoidant coping, treating it much like any other anxiety disorder. This should facilitate our secondary focus on anxiety. Key strategies include: psychoeducation, behavioral assessment, activity monitoring and structuring, activation of social networks, interpersonal effectiveness, and problem solving.
- **2.2.2. Treatment indicators. Compliance** is defined as attending a minimum of six sessions (reduced if patient has two consistent sessions of EPDS session-wise scores<10) over a period of four months unless a pregnancy- or COVID-related hiatus is experienced. Reasons for dropout will be recorded in the individual patient's treatment log (see SUMMIT Treatment Log Record Form, Appendix C Study Measures, pg 40) using a data capture and storage system called the Research Electronic Data Capture (REDCapTM). **Response** and **remission** will be defined as PHQ-9 of less than 10 and less than 5, respectively, at 3-months post-randomization. This period will be extended in the event that there is a hiatus to treatment due to significant perinatal-related life events (e.g., giving birth, obstetrical complications, COVID-19). Another indicator will include the estimation of comorbidity on both the EPDS and GAD-7.
- **2.2.3. Intervention Arms.** During regular operations participants will be randomized to one of four arms (Figure 2):

[figure not shown]

[figure not shown]
Figure 2. Intervention Arms

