#### 3.5. Statistical Analyses

**3.5.1.** Primary Analysis. Using SAS 9.4, primary analyses will be performed based on an intentto-treat basis. Two-sided significance levels of p<0.05 will be used for all analyses. Demographic (ethnicity, age, marital status) and other baseline variables (e.g., severity and chronicity) will be compared for potential differences between study groups using descriptive statistics (means, standard deviations, proportions) and the associated statistical tests (t-tests, chi-square tests). Those who drop out of the study will also be compared to those completing the study on baseline indices including maternal education and occupation. The primary outcome of noninferiority in EPDS scores will be compared between groups (telemedicine vs in-person, and specialist vs NSP) at 3-months using a t-test. The assessment period will be extended in the event that there is a hiatus to treatment due to significant perinatal-related life events (e.g., giving birth, obstetrical complications or COVID-19). One t-test will be run to assess this and compare modes (is telemedicine non-inferior to in-person). Another t-test will be run to assess this and compare agents (is non-specialist non-inferior to specialist). Each t-test will look at the confidence interval around the difference in EPDS scores (say between telemedicine and inperson), and see if the upper bound contains the 10% (provider) or 13% (modality) noninferiority margin (upper bound for the case in which we take the difference to be telemedicine minus in-person). We will conduct a sensitivity analysis to examine potential differences in baseline and outcome depressive symptoms and anxiety symptom scores to determine whether participants who were recruited and received treatment during the COVID-19 outbreak differed significantly from the larger sample.

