1.6.2. Primary Aim 2 (Telemedicine vs. In-Person) Comparison

The primary outcome measure is an EPDS mean score at 3 months post-randomization. The sample size calculation is based on an EPDS mean estimate of 7.93 (SD=4.68)³⁰. Using a non-inferiority margin of 13% (i.e., EPDS score of 1.03 in relation to the mean), and an alpha=0.05, we require an additional 268 IP participants ([Table 4](#)).

Table 4: Non-inferiority margin in relation to sample size for Phase 3 comparisons

Non-inferiority margin	Power	Sample size per primary question	Total sample size + 10% dropout*	Total sample size + 20% dropout
10%	80%	431	958	1078
13%	80%	241	536 (268 per group)	604
14%	80%	221	492 (246 per group)	556

*Current dropout rates are <10% at primary outcome of 3-months post-randomization

When combined with the 958 TM participants, this yields a total study sample size of N=1,226 which accounts for 10% loss to follow-up ([Table 5](#)).

Table 5: Primary aims and required sample sizes

Primary Aim [¥]	Non-inferiority Margin	Power	Required sample size + 10% drop out
SP vs. NSP [¥]	10%	88%	958 telemedicine
IP vs. Telemedicine	13%	80%	268 in-person*
	Total		N=1226*

[¥]We acknowledge that the in-person sample is contained in the first hypothesis. This will result in the SP vs NSP comparison having up to 88% power. *We will over-recruit to account for protocol deviations where participants were switched from in-person to telemedicine due to the COVID-19 pandemic.

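### SAP 3.4.1 calls an as-treated grouping 'per protocol'; no analysis set uses the Protocol's compliance definition, and for non-specialist vs specialist the second analysis nearly repeats ITT

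*SAP*

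**What the plan says.** SAP 3.4.1 runs all analyses twice: as "intent-to-treat (ITT, i.e., group that the participant was randomized to", and as "per protocol (i.e., group participant actually participated in". An asterisk on the second leads to a note: "The trial has n=21 protocol deviations". The footnote to SAP Table 5 describes "protocol deviations where participants were switched from in-person to telemedicine due to the COVID-19 pandemic". Neither document defines a per-protocol set in any other way.

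Protocol 2.2.2 has a compliance definition. Compliance "is defined as attending a minimum of six sessions" within four months. The session minimum is reduced after low session EPDS scores, and the period allows for a pregnancy- or COVID-related hiatus. This definition forms no analysis set. In the SAP, compliance is counted by arm (3.1) and listed among the covariates of interest: "timing of treatment, compliance, perceived support, and medication" (3.4.1).

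On precedence, Protocol 3.5.1 says "primary analyses will be performed based on an intentto-treat basis". The SAP gives one success rule, that the upper limit of the 95% interval must not exceed the margin. It does not repeat that ITT decides, and it does not say what follows if the two analyses disagree.

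**The concern.** In a non-inferiority comparison, anything that makes the arms more alike favours the claim. Women who attend few sessions get little of the treatment whose provider or mode is being compared, so keeping them tends to shrink a real difference. A per-protocol analysis is usually placed beside ITT to show whether the conclusion survives without them.

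The SAP's second analysis carries that name but answers a different question. It regroups women by what they received and removes nobody for low attendance. The recorded switches are of mode, so for NSP vs SP almost every woman stays in the same group as under ITT. A reader who sees both analyses agree on Aim 1 could take this as evidence that low attendance did not drive the result, when the second analysis could hardly have differed. Women who never started treatment took part in no group, so their place in this set is undefined.

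**Working it through.** **Inputs from the documents.** SD 4.68; margins 0.793 (provider, SAP Table 3) and 1.03 (mode, SAP 1.6.2); 958 TM and 268 IP, total 1,226; dropout allowance 10%; 21 deviations.

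**Assumptions.**
- The non-compliance rate is not given; the range used is 10% to 40%.
- Non-compliers show no difference between arms.
- The true difference among compliers equals the margin.
- The 95% interval is two-sided.
- All 21 deviations are IP-to-TM switches.

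**The plan's own figure.** n per group = 2 × SD² × (z for alpha + z for power)² / margin² = 2 × 4.68² × (1.645 + 0.842)² / 0.793² ≈ 431. This matches SAP Table 3, with a one-sided alpha of 0.05.

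**Evaluable numbers after 10% loss.**
- Provider: 1,226 × 0.9 / 2 ≈ 552 per group. SE = 4.68 × √(2/552) = 0.282.
- Mode: 958 × 0.9 ≈ 862 TM and 268 × 0.9 ≈ 241 IP. SE = 4.68 × √(1/862 + 1/241) = 0.341.

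**Dilution from low attendance.** With a non-compliant share c in both arms, the expected difference is margin × (1 − c). The chance of meeting the margin is Φ(c × margin / SE − 1.96). For provider at c = 20%: 0.2 × 0.793 / 0.282 = 0.563, and Φ(0.563 − 1.96) = 8.1%. The last two columns give power at a true difference of zero if non-compliers are excluded.

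| c | Wrong claim, provider | Wrong claim, mode | Power, provider | Power, mode |
|---|---|---|---|---|
| 0% | 2.5% | 2.5% | 0.80 | 0.855 |
| 10% | 4.7% | 4.9% | 0.76 | 0.82 |
| 20% | 8.1% | 8.8% | 0.71 | 0.77 |
| 30% | 13.2% | 14.6% | 0.65 | 0.71 |
| 40% | 20.2% | 22.6% | 0.59 | 0.65 |

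Regrouping by treatment received leaves the two wrong-claim columns essentially unchanged, because it removes no one for low attendance.

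**Switched women.** 21/268 = 7.8% of IP, or 21/1,226 = 1.7% of the trial.
- Under ITT, a true mode difference of 1.03 shrinks to 1.03 × (1 − 0.078) = 0.95. Regrouping restores it to 1.03 if switched women have the same prognosis as the rest.
- If their prognosis differs by 1 EPDS point, removing them from IP shifts the TM minus IP difference by 21/268 = 0.08. Adding them to 958 TM women shifts it by a further 21 × 0.922 / 979 = 0.02. The total is 0.10.
- If the comparison used 268 TM women, the second term is 21 × 0.922 / 289 = 0.067, and the total is about 0.145.

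**The case against.** Several points on the other side stand.

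- Protocol 3.5.1 already names ITT as the primary basis, so the deciding analysis is not wholly open. What is missing is a restatement in the SAP and a rule for discordant results.
- For TM vs IP, regrouping undoes the dilution caused by switching, so the as-treated analysis has some value.
- Compliance is not ignored: it is reported by arm and listed as a covariate. Neither use creates a population of women treated as planned.
- That low attenders stay in the set is inferred from the absence of any exclusion rule.
- Related analyses exist. Protocol 3.5.2 excludes women who left after the first session, but it does so under secondary analysis, following the child outcomes. The SAP's counterpart is in the child-development section (3.4.2.4). Neither is tied to the primary tests. SAP Table 6 brings women who never started into the ITT analysis, but it has no compliance-based set.
- A compliance-based set also departs from randomisation. The session exception depends on EPDS scores, the outcome instrument, so women who improve early with few sessions stay in while others with few sessions are removed.

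A reader might infer that the switches alone could decide Aim 2. The documents do not support that. A large shift needs a prognostic gap of around one SD or more, for which they give no basis. Most of the shift (0.08 of 0.10 per point) would also arise if the 21 women were excluded.

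**Conclusion.** The set is mislabelled, and a compliance-based per-protocol analysis of the primary outcome is missing. For NSP vs SP, the second analysis gives almost no information beyond ITT. At an assumed 10% to 40% non-compliance, the chance of wrongly declaring non-inferiority rises from 2.5% to about 5–20% (provider) and 5–23% (mode). 'Wrongly' here refers to the effect among compliers. These figures are upper illustrations: they shrink if non-compliers show part of the arm difference. The effect of moving 21 women is modest.

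Three stronger readings do not hold.

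- That the trial lacks its main non-inferiority safeguard. ITT is named as primary, and the as-treated set does address switching for Aim 2.
- That a loss diluted to just under the margin would pass. Success depends on the interval's upper limit. Suppose a true loss of 1.3 among treated women and 25% non-compliance. The expected difference is 1.3 × 0.75 = 0.975 and the upper limit is 0.975 + 1.96 × 0.341 = 1.64, well above 1.03. The chance of passing is about 3.6%.
- That non-inferiority should require both sets to meet the margin. That is a trade-off with a real cost in power, and neither document commits to it.

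**What to change.** In SAP 3.4.1:

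1. Rename the current set 'as-treated', keep it as supportive, and state how women who never started treatment are handled.
2. Add a per-protocol set: women who received their allocated mode and provider type and met the Protocol 2.2.2 compliance definition, analysed in the randomised arm. Pre-specify it as a sensitivity analysis for both primary aims, beside ITT.
3. State that ITT decides, in line with Protocol 3.5.1, and how a discordant per-protocol result will be reported and interpreted.
4. Report the number excluded and the reasons by arm, and note that the compliance exception depends on session EPDS scores.

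The cost is SAP wording and one further analysis from treatment-log data already collected. The per-protocol set is smaller: if 20% are excluded, power is about 0.71 (provider) and 0.77 (mode). It is also selected after randomisation. Both are reasons to keep it as a sensitivity analysis and not as a condition for the claim.

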#### 2.6. Sample Size

The primary outcome measure will be participant's EPDS mean score at 3 months after randomization; the assessment period will be extended in the event that there is a hiatus to treatment due to significant perinatal-related life events (e.g., giving birth, obstetrical complications, COVID-19) or to one week after the last session if participants complete treatment after the 3 month-post randomization period. The study is designed to be a noninferiority trial with four arms: telemedicine specialist, telemedicine non-specialist, in-person specialist, in-person non-specialist. The two primary hypotheses are that telemedicine will be non-inferior to in-person, and that non-specialist delivery agents will be non-inferior to specialist delivery agents. The sample size calculation is based on an EPDS mean estimate of 7.93 (SD=4.68). Using a non-inferiority margin of 10% (i.e., EPDS score of 0.79) in relation to the mean), and an alpha=0.05 for our first comparison (NSP vs. SP) we require 431 participants in each of the two groups to provide greater than 80% power. To account for 10% drop out, the sample size is inflated to N=958 (479 per group, NSP vs. SP). Using a non-inferiority margin of 13% (i.e., EPDS score of 1.03 in relation to the mean), and an alpha=0.05 for our second comparison (TM vs. IP), we require an additional 268 IP participants. When combined with the 958 TM participants, this yields a total study sample size of N=1,226 which accounts for 10% loss to follow-up. Previous randomized non-inferiority trials have demonstrated that a 14% non-inferiority margin can be considered clinically meaningful.

We are planning a final sample size of N=1,230, four more participants than the power calculation requires. The reason for this n=4 over recruitment, is to provide flexibility due to the fact that we do not receive each site's recruitment numbers until the end of each day. These statistics have been reviewed and approved by our study statistician.

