1.6.1. Primary Aim 1 (Specialist vs. Non-Specialist) Comparison

The primary outcome measure is an EPDS mean score at 3 months post-randomization. The sample size calculation is based on an EPDS mean estimate of 7.93 (SD=4.68)³⁰. Using a non-inferiority margin of 10% (i.e., EPDS score of 0.79 in relation to the mean), and an alpha=0.05, we require 431 participants in each of the two groups (SP, NSP) to provide greater than 80% power ([Table 3](#)). To account for 10% drop out, the sample size is inflated to **N=958** (479 per group, SP vs. NSP). All sample size calculations were run using PASS Version 12³¹.

Table 3: Power Analysis of a Non-Inferiority Test of the Difference of Two Means

Power	N1/N2	Non-Inferiority Margin (NIM)	Actual Difference	Significance Level (Alpha)	Beta	Standard Deviation 1 (SD1)	Standard Deviation 2 (SD2)
0.80022	431/431	0.793	0.000	0.05000	0.19978	4.680	4.680

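### Both primary comparisons are sized at one-sided 5% but judged on a 95% confidence interval, and the 241 per group in Table 4 does not reproduce, so the stated powers of 80%, 88% and 80% are not those of the planned tests

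*SAP*

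**What the plan says.** **Decision rule.** SAP 3.4.1 gives one criterion for both primary tests: "a successful result will be based on the upper bound of the 95% confidence interval being less than or equal to the non-inferiority margin". It does not say whether the interval is one- or two-sided. Protocol 3.5.1, in the paragraph that also describes comparing the interval with the margin, states: "Two-sided significance levels of p<0.05 will be used for all analyses".

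**Aim 1 size.** SAP 1.6.1 uses a "non-inferiority margin of 10% (i.e., EPDS score of 0.79 in relation to the mean), and an alpha=0.05", without giving the sidedness. Table 3 then reports 431/431, margin 0.793, SD 4.68, true difference 0 and power 0.80022. Protocol 2.6 repeats that "we require 431 participants in each of the two groups to provide greater than 80% power". Allowing for 10% dropout gives 479 per group, 958 in total. A footnote to SAP Table 5 notes that in-person participants also count towards this comparison and adds: "This will result in the SP vs NSP comparison having up to 88% power".

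**Aim 2 size.** SAP 1.6.2 uses a 13% margin (1.03 points) and alpha 0.05. Table 4 gives 241 per group for 80% power, entered after 10% dropout as "536 (268 per group"). Table 5 combines 268 in-person with 958 telemedicine participants, 1,226 in all, and again shows 80%. SAP 3.4.1 describes the Aim 2 comparison as 268 in each group.

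**The concern.** In a non-inferiority test, requiring the upper limit of a two-sided 95% interval to lie at or below the margin is a one-sided test at 2.5%. A sample size computed at one-sided 5% corresponds to a two-sided 90% interval. If the plan sizes on one and decides on the other, its powers belong to a test that will not be carried out.

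Two things are at stake. The first is the accuracy of the powers and of the in-person target, since 268 comes directly from the 241 in Table 4. The second is the error rate. A result whose upper limit clears the margin at 90% but not at 95% is a success at the sizing alpha and a failure under the written rule. If that choice stays open until the data are seen, the one-sided error per test could move from the 2.5% of the written rule to 5%. The plan also makes no multiplicity adjustment across its two primary hypotheses.

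**Working it through.** **Inputs.** Mean 7.93, SD 4.68, true difference 0, 10% dropout (SAP 1.6.1 and 1.6.2). Margins: 10% = 0.793; 13% = 0.13 × 7.93 = 1.0309; 14% = 1.1102.

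**Formulas.** Required n per group ≈ 2(z₁₋α + z₀.₈₀)²(SD/margin)². Power ≈ Φ(margin/SE − z₁₋α), with SE = SD·√(1/n₁ + 1/n₂). The powers and final n below use the non-central t, which differs from these by about one participant or a fraction of a percentage point. The squared sum of z-values is (1.645 + 0.842)² = 6.183 at one-sided 5% and (1.960 + 0.842)² = 7.849 at one-sided 2.5%.

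**Step 1: reproduce Table 3.** At one-sided 5%, n = 2 × 6.183 × (4.68/0.793)² = 430.7, so 431. At 431 per group, SE = 0.3188 and margin/SE = 2.487. Power is Φ(2.487 − 1.645) = 0.800, matching the stated 0.80022. At one-sided 2.5% it is Φ(2.487 − 1.960) ≈ 0.70 (0.7001 by t), and 80% needs 548 per group (609 with dropout, 1,218 in total). Table 3 is therefore a one-sided 5% calculation.

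**Step 2: reproduce the 88%.** 1,226 × 0.9 = 1,103, about 552 per group. SE = 0.2817 and margin/SE = 2.815. Power is 0.879 at one-sided 5%, matching 88%, and 0.803 at one-sided 2.5%.

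**Step 3: check Table 4.**

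| Margin | Stated n per group | Needed, one-sided 5% | Needed, one-sided 2.5% |
|---|---|---|---|
| 10% (0.793) | 431 | 431 (432 by t) | 548 |
| 13% (1.0309) | 241 | 256 | 325 |
| 14% (1.1102) | 221 | 221 | 280 |

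The 10% and 14% rows reproduce at one-sided 5%. The 13% row fits neither alpha. To obtain 241 at one-sided 5%, the margin would have to be about 1.06 (13.4% of 7.93) or the SD about 4.55. With 10% dropout, 256/0.9 gives 285 per group, not 268, and 325/0.9 gives 362.

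**Step 4: Aim 2 power for the two comparisons the SAP describes.**

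| Evaluable TM / IP | SE | One-sided 5% | One-sided 2.5% (95% CI rule) |
|---|---|---|---|
| 241 / 241 (268 per group less 10%) | 0.4263 | 77.9% | 67.5% |
| 862 / 241 (958 and 268 less 10%) | 0.3410 | 91.6% | 85.6% |

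At the planned 10% dropout, none of the four cells is the stated 80%.

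**Step 5: what alpha 0.05 means elsewhere in the SAP.** Section 3.4.2.4 requires 393 per group for a 3-unit difference with SD 15, 80% power and alpha 0.05. That is 2 × 7.849 × (15/3)² = 392.4, so 393, a two-sided 5% calculation. The SAP thus uses the same alpha of 0.05 in two senses without saying so.

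**The case against.** The strongest reply is that no sentence in either document gives 2.5% or calls the primary interval two-sided. SAP 3.4.1 mentions a two-sided level only for the secondary superiority hypotheses, and SAP 1.6 separates superiority p-values from the non-inferiority interval rule. A one-sided 95% upper bound would agree with alpha 0.05, and the 80% and 88% for Aim 1 would then stand. This reading is possible, but it is nowhere stated, it departs from the ordinary meaning of a 95% interval, and it conflicts with Protocol 3.5.1. Even if it is accepted, the 13% row is still wrong and the Aim 2 groups are still described in two ways.

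The second reply is that the low powers belong to subsets that will not be the analysis. SAP 3.4.1.1 says the analyses use the entire sample. On that basis Aim 1 keeps 80.3% under the stricter reading, so the claim of more than 80% survives for the full sample. Aim 2 with all telemedicine participants has 85.6%, above the stated 80%. Against 862 telemedicine participants, about 200 evaluable in-person participants would be enough. With equal groups of about 552, which SAP 1.5 gives as the aim of the weighted randomization, Aim 2 power would be 95.5%. This stands. It limits the consequence but does not make the printed figures right.

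Third, the 241 error is small taken alone: 15 per group and about two percentage points. It disappears at one-sided 5% if dropout is 4.5% or less (256 of 268), and with no dropout 268 per group gives 81.6%. SAP Table 4 notes that dropout is running below 10%. That is fair, but the table is headed as allowing for 10%, and under the 95% interval rule 268 per group with no dropout still gives only 72.1%.

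**Conclusion.** The concern holds. The sizing alpha and the decision rule disagree, and one table row is wrong at either alpha. With the 95% interval read as two-sided, a true difference of 0, SD 4.68 and no allowance for clustering by provider:

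- Aim 1 at 431 per group has 70.0%, not more than 80%.
- Aim 1 on the full sample has 80.3%, not 88%.
- Aim 2 at 241 per group has 67.5%, not 80%, whereas with all telemedicine participants it has 85.6%.

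Most of the gap comes from the alpha mismatch; the 241 error adds about two points. For Aim 2, one-sided 5% is inferred from the neighbouring rows of Table 4, because 241 itself fits neither alpha. The trial as a whole is not shown to be underpowered: full-sample power is about 80% or better for both aims. The fault lies in the stated powers, the derivation of the in-person target and the unsettled error rate for the primary claim. If a one-sided 95% bound was intended, the Aim 1 figures stand and only the Aim 2 faults remain.

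**What to change.** Choose one error rate and state it identically in Protocol 2.6 and 3.5.1 and in SAP 1.6 and 3.4.1.

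1. Preferably keep the interval, specify it as two-sided 95%, and restate all powers at one-sided 2.5%. Aim 1 then has about 80% on all randomised participants less 10%. Delete the claim of more than 80% at 431 (479 with dropout) per group, or restate it as 70%.
2. If one-sided 5% was intended, write a two-sided 90% interval (or a one-sided 95% bound) into both documents before any unblinded outcome data are seen, and exempt the non-inferiority tests from the protocol's two-sided 5% statement.
3. Correct the 13% row of Table 4: 256 per group (285 with dropout) at one-sided 5%, or 325 (362) at one-sided 2.5%, both for equal groups.
4. State whether Aim 2 compares 268 with 268 or all telemedicine with all in-person participants, and give the power for that comparison (85.6% for 862 against 241 under the 95% rule). Align Table 5 and SAP 3.4.1.

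The cost is wording in two documents and corrections to the SAP's sample-size tables. The Aim 1 powers fall, and Aim 2 rises above 80% if all telemedicine participants are used. No additional recruitment is required.
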